6.2 Randomization

Eligibility work-up will include a complete blood count, serum chemistries, PSA, and radiographic studies (of involved sites) and bone scan (unless PET indicated). Once a signed informed consent has been obtained and after confirming patient eligibility, the lead data coordinator will assign a unique Study ID Number.

Treatment must not commence until the patient has received his identification number.

Stratification:

Subjects who meet eligibility criteria and qualify for enrollment will be stratified according to the following:

- 1) Institution
- 2) Initial treatment with surgery vs. radiation therapy
- 2) Prior hormonal therapy vs. no prior hormonal therapy
- 3) PSADT <6 months vs. 6-14.9 months

Process for Randomization:

The research team will utilize an interactive web response system (IWRS) to obtain the patient's randomization assignment. The lead coordinator will enter demographic and baseline characteristics in IWRS. The lead coordinator will obtain the patient's randomization assignment from the IWRS and appropriately notify the study site. Randomization will be 1:1 for SABR: SABR + Radium-223 arms and be stratified as above. Minimization approach will be applied to ensure balanced assignment to each treatment arm. The **ON STUDY date for protocol entry** will be the day that the study subject is randomized. Within 30 days from the date of randomization, is considered DAY 1 of SABR and/or SABR + Radium-223 Arm.

All institutions should allow 48 hours for patients to be randomized from the time they provide all eligibility documentation.

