9.5.5 Clinical Response Parameters

Progression is a composite endpoint defined from the Prostate Cancer Working Group 2 (PCWG2) criteria for metastatic castrate resistant prostate cancer (mCRPC) (75) and our previous trials in a population of men with biochemical failure without metastases (72-74). Progression will be defined as either: 1) a $\geq 25\%$ increase in PSA from nadir (and by ≥ 2 ng/mL), requiring confirmation ≥ 4 weeks later (PCWG2 criteria); and/or, 2) clinical/radiographic-progression defined as symptomatic progression (worsening disease-related symptoms or new cancer-related complications), or radiologic progression (on CT scan: $\geq 20\%$ enlargement in sum diameter of soft-tissue target lesions [RECIST 1.1 criteria]; on bone scan: ≥ 1 new bone lesions), initiation of ADT or death due to any cause, whichever occurs first. Death is considered a severe adverse event here.

Progression Free Survival (PFS) is defined as the time from starting treatment to the time of progression as defined above. Subjects who do not progress will be censored at the time of the last contact.

ADT Free Survival (ADT-FS) is defined as the time from starting treatment to the time of initiation of palliative ADT. ADT will typically be initiated on tumor progression and/or development of new metastases. Subjects who do not start ADT will be censored at the time of the last contact.

Time to Progression (TTP) is defined as the time from starting treatment to the time of first documented tumor progression or new lesions by CT and/or bone scan or initiation of ADT. Subjects who do not progress will be censored at the time of the last contact. In addition, death from any cause will also be censored.

Time to New Metastasis (TNM) is defined as the time from starting treatment to the time of a new documented tumor metastasis by CT and/or bone scan. Subjects who do not progress will be censored at the time of the last contact.

Overall Survival (OS) is defined as the time from starting treatment until death due to any cause. For subjects who do not die, time to death will be censored at the time of last contact.

Locoregional Control (LRC) is defined as the time from starting treatment until local and/or regional relapse is documented

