14.2 Sample Size/Accrual Rate/Follow-Up

The primary endpoint will be progression-free survival (PFS). Data from STOMP and ORIOLE on this patient population indicate that $\geq 50\text{-}60\%$ would show progression as defined above within a 12-month period from SABR, and a median PFS around 10 months. (72-74). We hypothesize that the addition of radium-223 will be able to reduce the risk of progression by 50%. A sample size using a 1:1 randomization scheme of 30 patients per arm will provide 80% power to detect an increase of median PFS from 10 months to 20 month (corresponding to hazard ratio 0.5) with type I error = 0.1, using one-sided log-rank test. The calculation assumes 18 months of accrual time with an additional follow-up of 12 months after the last patient is randomized. To account for 5% early drop out, we will randomize a total of 64 patients (32 per arm).

There will be no interim analysis for futility, since the progression endpoint will not have been reached by a meaningful number of patients before full accrual.

Follow-up (Every 3-6 months for 24 months or until death)

Patients will be followed for 2 years after Day One of trial or until death. Patients withdrawn from the study because of AEs will be followed until the adverse event has either resolved or stabilized. Reasons for premature withdrawal should be determined and noted.

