14.4 Analysis of Primary Objective

This is a randomized, Phase II trial of SABR *versus* SABR + Radium-223 in oligometastatic hormone sensitive prostate cancer patients. Minimization approach (77) will be applied to ensure balanced assignment to each treatment arm by stratification factors: 1) Institutional; 2)Initial treatment with surgery vs. radiation therapy; 3) Prior hormonal therapy vs. no prior hormonal therapy; and 4) PSADT <6 mos vs. 6-14.9 mos. Baseline PSA level is defined as that measured Day 1 following randomization. Progression is defined as per section 9.6.2.

The primary outcome of interest is PFS, defined as the time from the date of randomization to the date of disease progression or death, whichever happens earlier. For those who are alive and do not have progressive disease, PFS will be censored at the time of the last scan. Kaplan-Meier method will be used to summarize PFS and log-rank test will be used to compare PFS between the two arms. The analysis population includes all randomized subjects based on intent-to-treat principle.

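### The primary log-rank test uses none of the four minimisation factors; if PSADT is prognostic, it is conservative and loses power that stratifying on PSADT would recover

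*Combined protocol and SAP*

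**What the plan says.** Section 6.2 lists institution, initial treatment (surgery or radiation), prior hormonal therapy (yes or no) and PSADT ("PSADT <6 months vs. 6-14.9 months"), and adds: "Minimization approach will be applied to ensure balanced assignment to each treatment arm". Section 14.4 repeats the list and says that minimisation gives "balanced assignment to each treatment arm by stratification factors".

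The same section then describes the primary analysis of PFS in all randomised men: "Kaplan-Meier method will be used to summarize PFS and log-rank test will be used to compare PFS between the two arms". Section 14.2 adds only the error rate and direction: "with type I error = 0.1, using one-sided log-rank test". Its sample-size statement is that "30 patients per arm will provide 80% power to detect an increase of median PFS from 10 months to 20 month". It equates this gain with halving the hazard.

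Neither section names strata, covariates, a Cox model or a re-randomisation test for PFS, and no other section does so.

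**The concern.** Minimisation makes the arms more alike on PSADT than chance would. If PSADT predicts PFS, the difference between arms then varies less from trial to trial than the plain log-rank variance assumes. The test rejects too rarely under the null and loses power under the alternative.

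The documents give no hazard ratio for PSADT, but a link with PFS is plausible. The plan restricts entry by PSADT and balances on it. One route to progression in section 9.5.5 is a PSA rise of at least 25%, an "increase in PSA from nadir (and by" at least 2 ng/mL), confirmed at least 4 weeks later. At constant growth, the time to that rise is proportional to PSADT.

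The trial has little slack, because the design sits almost exactly at 80% power. The wording also leaves a choice open. With four factors labelled as stratification factors, an analyst could later stratify on none, one or all of them, and the power differs widely between those choices. The trial is not blinded, so the choice should be fixed in advance.

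**Working it through.** **1. The plan's own figure.** Inputs from 14.2: medians 10 and 20 months, 30 men per arm, one-sided 0.10, 18 months of accrual, 12 more months of follow-up. With exponential PFS and uniform accrual, the event probability is 1 − [exp(−12λ) − exp(−30λ)]/(18λ), with λ = ln 2/median.

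- Control: 1 − (0.4353 − 0.1250)/1.2477 = 0.751
- Experimental: 1 − (0.6598 − 0.3536)/0.6238 = 0.509
- Expected events: 30 × (0.751 + 0.509) = 37.8
- Power (Schoenfeld): Φ(√37.8 × ln 2/2 − 1.2816) = Φ(0.850) = 0.802

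The 80% reproduces for a plain test with no prognostic heterogeneity. With all 64 men, the same formula gives 40.3 events and power 0.821.

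**2. Why PSADT may matter.** At constant growth, months to the PSA criterion = PSADT × log2(max(1.25, 1 + 2/nadir)). From a nadir of 2 ng/mL the last term is log2(2) = 1, so the time is 6 months at PSADT 6 and 14.9 months at PSADT 14.9. This assumes that the pre-treatment PSADT carries over after treatment.

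**3. Simulation.** Common inputs: 64 men, minimisation on the four factors, exponential PFS with marginal control median 10 months, treatment hazard ratio (HR) of 1 or 0.5 within PSADT groups, uniform 18-month accrual, analysis at month 30, rejection at z > 1.2816, 20,000 trials per setting (Monte Carlo SE about 0.002 for type I error, 0.003 for power). Assumed, because the documents do not give them: the PSADT HR, 4 sites, a minimisation coin of 0.8, half the men with PSADT under 6 months, and no other prognostic factor. Run A caps follow-up at 24 months. Run B, programmed independently, has 5% drop-out by month 30 and no cap. Each cell is plain / PSADT-stratified.

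| PSADT HR | Type I error, A | Type I error, B | Power, A | Power, B |
|---|---|---|---|---|
| 1 | – | 0.105 / 0.104 | 0.812 / 0.807 | 0.813 / 0.808 |
| 1.5 | – | 0.097 / 0.102 | 0.800 / 0.802 | 0.802 / 0.802 |
| 2 | 0.097 / 0.107 | 0.089 / 0.099 | 0.785 / 0.801 | 0.787 / 0.802 |
| 3 | 0.084 / 0.103 | 0.084 / 0.104 | 0.746 / 0.799 | 0.741 / 0.796 |

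A third simulation (15,000 trials per setting) gave type I error 0.093 / 0.101 and power 0.785 / 0.803 at HR 2, and 0.088 / 0.106 and 0.749 / 0.802 at HR 3.

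**4. Cause.** In run B the null variance of the plain z statistic was 0.938 at HR 2 and 0.857 at HR 3, not 1. The implied sizes are 1 − Φ(1.2816/√0.938) = 0.093 and 1 − Φ(1.2816/√0.857) = 0.083, in line with the table. With 1:1 allocation that ignored the factors, the plain test held its size (0.104 and 0.098), so the conservatism comes from the balancing. It still lost power there: 0.784 against 0.803 at HR 2, and 0.727 against 0.786 at HR 3.

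**5. Other settings.** Run A was repeated with 60 men and no cap, with the other binary factors prognostic (1.5 for prior hormonal therapy, 1.2 for initial treatment), and, at HR 2 and 3, with 30% or 70% of men under 6 months. The gain from stratifying was 1.1 to 2.0 points at HR 2 and 3.7 to 5.5 at HR 3. The lowest gain in run B at HR 2 was 0.9 points (0.787 against 0.796, 30% under 6 months). Plain-test power in run A ranged over 0.754–0.792 at HR 2 and 0.722–0.768 at HR 3; stratified power over 0.774–0.803 and 0.773–0.805.

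**6. Stratifying on more factors.** The three binary factors together (2 × 2 × 2 = 8 strata) gave power of 0.72–0.76. All four, with 4 sites, make 32 cells, or 64/32 = 2 men per cell on average, and gave 0.54–0.60. Run B gave about 0.58 (4,000 trials).

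**The case against.** The plan is consistent and valid: 14.2 powers a log-rank test, 14.4 uses one, and the plain test errs on the safe side. The harm depends on a PSADT hazard ratio that the documents do not give; the gain is nil at 1.5 and slightly negative at 1. The PSA illustration picks one nadir and compares a cut-point with the far end of the other category, while progression also counts imaging, symptoms, ADT start and death. All of this stands, and it is why the size can only be given as a range.

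Two further points are technical. First, much of the gap is test size. When both tests were calibrated to exactly 0.10 (6,000 trials per setting), power was 0.795 plain against 0.806 stratified at HR 2, and 0.785 against 0.788 at HR 3. That is correct, and the stratified test can run slightly above nominal (up to 0.107 in run A, and 0.109 at HR 3 in this calibration run). But the trial will use the fixed critical value, where the plain test's conservatism costs real power.

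Second, the simulations set the treatment HR at 0.5 within PSADT groups, so the marginal HR drifts to 0.51 at PSADT HR 2 and 0.54 at HR 3. Part of the shortfall does come from that choice. However, halving an exponential hazard in each group doubles every event time, so the medians stay at 10 and 20 months, as 14.2 states.

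**Conclusion.** The concern holds. As written, the primary test ignores a factor that the trial already balances on. If PSADT carries a hazard ratio of 2 to 3 for PFS, the plain test has less than 80% power even when the stated medians are true. Stratifying by PSADT recovers most of the loss: about 1 to 2 points at 2, and about 4 to 5.5 points at 3. There is no gain at 1.5.

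The direction is well supported, because separately run simulations agree. The size rests on the assumed PSADT effect, exponential PFS, the number of sites and the minimisation settings. The stated 80% is not a miscalculation, and the false-positive rate of the planned test is not inflated. It is a cheap efficiency gain worth taking.

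**What to change.** In section 14.4, name the primary test as a one-sided 0.10 log-rank test stratified by PSADT category at randomisation (under 6 against 6–14.9 months) and by nothing else. Take the hazard ratio and its confidence interval from a Cox model stratified the same way, labelled as conditional on PSADT. Keep the unstratified log-rank test as a sensitivity analysis and the Kaplan-Meier medians as the marginal summary. Do not add institution or the other factors as strata, for the reason shown in step 6. Make the change before the arms are compared.

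The cost is two sentences and no new data, since PSADT category is already collected for minimisation. The downsides are 0.3 to 0.8 points of power if PSADT has no prognostic value, a type I error that may sit slightly above 0.10, and a hazard ratio that must be reported beside the marginal medians because it is conditional on PSADT.

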14.5 Analysis of Secondary Objectives

- For safety analysis, adverse events will be summarized by type and grade.
- Kaplan-Meier (KM) estimates will be used to summarize ADT-free survival (ADT-FS), time to locoregional progression (TTLP), time to distant progression (TTDP), time to new metastasis (TNM) and duration of response over time. The median PFS, ADT-FS, TTLP, TTDP TNM and duration of response will be reported.
- The efficacy of SABR + Radium-223 in men with oligometastatic disease will also be determined by measuring local control of each lesion at 12-months.

Each metastatic lesion will be considered a target lesion and independently evaluated for response using RECIST 1.1 or bone scan evaluation criteria above. The lesion will be coded as being locally controlled if it is considered stable radiographic disease or if there is evidence of a partial or complete response. Local control assessment will start at three months following randomization and continuous assessment will be pursued during the follow-up period. The proportion of the lesions that have a stable or better response will be estimated using generalized estimating equation.

- Quality of life will be assessed using the Brief Pain Inventory form. An overall score will be calculated pre-treatment and at the time of the 2nd radiologic reassessment. The change in score will be evaluated with a paired t-test.

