6.15 Withdrawal from Study

In accordance with the Declaration of Helsinki, patients have the right to withdraw from the study at any time for any reason, without prejudice to their medical care. The investigator also has the right to withdraw patients from the study for any of the following reasons:

- Subject withdraws consent for follow-up.
- Subject is lost to follow-up.
- Study is terminated for any reason.
- Occurrence of AEs, if discontinuation of study medication is considered necessary by the Investigator and/or patient.
- Lack of patient compliance.
- Protocol violation.
- Progressive disease as defined in section 9.5.5.

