10.3 Potential Adverse Events

Signs and symptoms of disease progression are not considered AEs. The development of a new cancer should be regarded as an AE. New cancers are those that are not the primary reason for administration of study treatment and have been identified after inclusion of the patient into the clinical study.

Because patients are receiving standard treatments, which are not part of this study, their treating physician will be counseling them on the risk of their treatments, including the risk of surgery, radiation therapy, and/or chemotherapy, whichever is appropriate for the type and the stage of their cancer. The procedures related to the study are phlebotomy, SBRT, and Radium-223 administration.

Phlebotomy can cause pain, bleeding, and rare needle site infection.

Reporting: All patients will be seen during the required protocol and calendar time-points, by their radiation oncologist or study team member, during the entirety of the trial. Any observations during the entirety of the study (2 years) will be recorded and should include attention toward the following potential side effects:

- Anal hemorrhage, colitis, constipation, diarrhea, fecal incontinence, hemorrhoids, nausea, proctitis, rectal hemorrhage, vomiting
- Anorexia, anxiety, and/or insomnia
- Bladder spasms, hematuria, urinary frequency, urinary incontinence, urinary retention, urinary tract pain, urinary urgency, erectile dysfunction
- Dermatitis radiation
- Fatigue and/or pain
- Hot flashes
- Bone Pain
- Neutrophil count decrease and/or platelet count decrease

Any and ALL additional adverse events should be recorded, even if not listed in the above potential side effects.

10.4 Stereotactic Body Radiation Treatment (SBRT)/Stereotactic Ablative Radiation Treatment (SABR)

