10.5.1.2 Reporting SAEs at Multi-Site/Participating Institutions

A subject's AEs and SAEs will be recorded and reported from the signing of the ICF up to at least 30 days after completing salvage radiotherapy. The investigator must instruct the subject to report AEs and SAEs during this time period.

Subjects with evidence of Xofigo related toxicity at the post-treatment follow-up visit will be followed via telephone contact or weekly visits until the drug- related toxicity has resolved. Additionally, the collection of all skeletal related events will be collected for 2 years. Adverse events should be based on the signs or symptoms detected during the physical examination and on clinical evaluation of the subject. In addition to the information obtained from those sources, the subject should be asked the following nonspecific question: "How have you been feeling since your last visit?" Signs and symptoms should be recorded using standard medical terminology. Any unanticipated risks to the subjects must be reported promptly to the IRB/IEC. In the event of an adverse event the first concern will be for the safety of the subject.

All AEs and SAEs must be recorded on source documents. All AEs and SAEs for subjects who meet inclusion and exclusion criteria will be recorded in the CRFs and submitted to the lead site. The investigator must follow up on all AEs and SAEs until the events have subsided, returned to baseline or, in case of permanent impairment, until the condition stabilizes.

Additional reporting is required for SAEs as follows:

- SAEs that are fatal and possibly protocol related should be reported by phone to the Protocol Chair immediately upon knowledge of the event.

Each participating site is responsible for evaluating and completing any additional reporting to their local IRB according to local IRB guidelines.

All SAEs, regardless of causality to study drug and/or administration device, will be reported promptly to the Coordinating Center (e-mail: [contact] and [contact]), within 24 hours of recognition of the event. If this falls on a weekend or holiday, an email notification is acceptable but must be followed by an SAE reporting form on the next business day.

CRO Coordinating Center

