14.1.2 Secondary Objectives

- To describe the toxicity of SABR and SABR + Radium-223 delivered for the population enrolled using grading with CTCAE v. 4.0
- To determine local control at 12-months after SABR and SABR + Radium-223 in patients with oligometastatic disease.

- To assess time to locoregional progression, time to distant progression, time to new metastasis and duration of response after randomization to SABR *versus* SABR + Radium-223.
- To assess ADT-free survival (ADT-FS) of this patient population after randomization defined as the time interval between the day of randomization and the initiation of ADT. ADT will typically be initiated on progression and/or development of new metastases.
- To assess quality of life following SABR *versus* SABR + Radium-223 arms. Brief Pain Inventory form which will be filled out by the patient at the treatment response intervals outlined above.

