14.6 Evaluation of Toxicity

All patients who receive at least one fraction of SABR and Radium-223 will be evaluable for toxicity from the time of their first treatment for SABR and Radium-223.

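### The adverse-event summary has no end of window, no time at risk and no split at ADT start, so by-arm counts are not like-for-like if radium-223 delays progression

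*Combined protocol and SAP*

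**What the plan says.** - **Objective.** Section 14.1.2: "To describe the toxicity of SABR and SABR + Radium-223 delivered for the population enrolled". The synopsis and section 3.3 name only SABR + Radium-223.
- **Analysis.** Section 14.5: "For safety analysis, adverse events will be summarized by type and grade". Section 14.6 adds that treated men "will be evaluable for toxicity from the time of their first treatment for SABR and Radium-223", which is a start without an end. Neither section mentions time at risk, events after ADT start, or the five attribution levels of section 10.2.4.
- **Length of collection.** Section 10.3: "Any observations during the entirety of the study (2 years) will be recorded". Both study calendars require adverse-event documentation at months 18 and 24 (footnote W for the SABR arm, footnote Z for the combination arm). Section 10.5.1.2, however, has events "recorded and reported from the signing of the ICF up to at least 30 days after completing salvage radiotherapy".
- **After progression.** Sections 6.10 and 14.2 follow men for 2 years (14.2 adds death as an end). Section 6.11 lists progression among the criteria for removal, and section 6.15 lists "Progressive disease as defined in section 9.5.5" among the reasons for which an investigator may withdraw a man.
- **ADT.** Section 9.5.5: "ADT will typically be initiated on tumor progression and/or development of new metastases". Section 4.5 acknowledges that ADT has significant adverse effects of its own.

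**The concern.** The design expects the arms to progress at different speeds, and progression changes what is observed. If adverse-event recording ends there, the slower-progressing arm is watched for longer and gathers more events of every kind. If recording continues, the faster-progressing arm spends more of the 2 years on ADT. Several events that section 10.3 asks sites to look for (hot flashes, erectile dysfunction, insomnia, fatigue) can then reflect ADT rather than study treatment. A table of counts by type and grade cannot separate these effects from the toxicity of SABR or radium-223. At stake is how harm is read beside benefit, since the imbalance is largest when the trial succeeds.

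**Working it through.** **Inputs.** Median PFS 10 v 20 months, 30 men per arm, one-sided type I error 0.1, 18 months of accrual plus 12 months of follow-up, 32 per arm randomized (section 14.2). Median ADT-free survival of 21 months after metastasis-directed therapy in a cited randomized phase II trial (section 4.5). Observation of 24 months (sections 6.10 and 14.2). Assumed: exponential times, with λ = ln 2 / median.

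**Reproducing the plan's own figure.** The event probability is 1 − [exp(−12λ) − exp(−30λ)]/(18λ), which is 0.751 and 0.509. Then 30 × (0.751 + 0.509) = 37.8 events. Power is Φ(√(37.8/4) × ln 2 − 1.282) = 0.80, as stated. The SABR median also implies 1 − 2^(−12/10) = 56% progressed by month 12, within the 50–60% quoted in section 14.2. The exponential model therefore fits the plan's own assumptions. The plan gives no figure for the adverse-event summary.

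**Time before and after progression.** Share progressed by T is 1 − exp(−λT). Mean progression-free time within T is (1 − exp(−λT))/λ. Mean post-progression time is T minus that.

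| | SABR | Combination | Ratio |
|---|---|---|---|
| Progressed by 24 months | 81% | 56% | |
| Mean progression-free months within 24 | 11.7 | 16.3 | 1.39 (combination higher) |
| Mean post-progression months within 24 | 12.3 | 7.7 | 1.60 (SABR higher) |
| Progressed by 6 months | 34% | 19% | |
| Mean progression-free months within 6 | 4.9 | 5.4 | 1.10 (combination higher) |

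**Reading (a): observation stops at progression.** Give both arms the same background event rate r per month. The share with at least one event is r/(r+λ) × (1 − exp(−(r+λ)×24)).
- r = 0.02 (assumed): 20% v 27%.
- r = 0.10 (assumed): 58% v 71%.

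This is an apparent excess of 7 to 13 points in the combination arm with no true difference.

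**Reading (b): observation runs to 24 months.** Suppose 30% to 70% of men on ADT have an ADT-related event (assumed).
- ADT at every PFS event, the upper bound: 81% v 56% exposed, 12.3 v 7.7 mean months. Excess in the SABR arm is 0.30 to 0.70 × (0.811 − 0.565) = 7 to 17 points.
- Half of progressors start ADT: 41% v 28% exposed. Excess is 0.30 to 0.70 × 0.123 = 4 to 9 points.
- ADT-free survival with a median of 21 months, doubling to 42 with radium (assumed): 55% v 33% exposed, 7.4 v 4.2 mean months. Excess is 0.30 to 0.70 × 0.220 = 7 to 15 points.

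**Would a short common window suffice?** It narrows the imbalance (ratio 1.10 at 6 months) but does not remove it. Discarding post-ADT events without a time denominator would recreate it, because the arm that starts ADT sooner is then observed for less time. Length matters too. A first infusion at four weeks (section 6.8) and five 4-week intervals put the sixth at Day 28 + 140 = 168. One four-week delay (section 6.11) makes it Day 196. A window of Day 181 plus 30 ends at Day 211, only 15 days later, if Day 181 is counted from randomization.

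**The case against.** The case against has weight.

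- **Collection is nominally common.** Both arms have 2 years of follow-up and the same month-18 and month-24 requirement. The minimum in section 10.5.1.2 is a floor, so it does not forbid longer collection. This stands. The gap is in the analysis window and in passages that point sites to different end dates.
- **The objective is descriptive.** Section 14.5 names no test and does not say by arm, and listing by type already shows hot flashes apart from marrow or bowel events. This stands in part. Section 14.1.2 names both arms of a randomized trial, so readers will compare them, and fatigue or insomnia cannot be assigned by type alone.
- **ADT need not start at a PFS event.** A confirmed PSA rise of at least 25% and 2 ng/mL counts as progression (section 9.5.5), while section 6.12 describes biochemical progression, for starting standard treatment, as PSA above 50 ng/ml. The 21-month ADT-free median against a PFS of about 10 months points the same way. This stands, so 12.3 v 7.7 months is an upper bound.
- **Leaving at progression is not established.** Section 6.15 gives a right to withdraw, not a duty, although section 6.11 lists progression under removal. Reading (a) is a possibility.
- **Attribution is recorded** (sections 10.2.4 and 10.5.1.1). It could help, but it is not in the planned summary, and the trial is unblinded.
- **A 2-year table that includes later therapy is a legitimate treatment-policy summary.** True, but the plan does not define it as one.

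**Conclusion.** The concern holds as a gap in the analysis plan. As written, adverse-event counts would mix study-treatment toxicity with unequal observation (11.7 v 16.3 months) or unequal ADT exposure (at most 12.3 v 7.7 months, about 7.4 v 4.2 under the slower-ADT assumption). The direction depends on a follow-up rule that the documents leave open. The sizes rest on exponential times, the hypothesised 10 v 20 month medians, and assumed event rates.

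A reader might infer that the harm table is certain to mislead in a known direction, or that it cannot serve the toxicity objective at all. The documents do not support either. The two mechanisms run in opposite directions, both vanish on average if PFS is equal, the objective is to describe, and collection is nominally the same in both arms. The primary test and the sample size are unaffected. The change should be made because it is nearly free and because the imbalance grows with the treatment effect.

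**What to change.** In sections 14.5 and 14.6:

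1. Reconcile section 10.3 and the calendar footnotes with section 10.5.1.2, and sections 6.11 and 6.15 with sections 6.10 and 14.2, so that one adverse-event observation period applies to both arms whatever the progression status. This concerns data collection, not treatment.
2. Keep a by-arm 2-year table of worst grade per man, label it as the treatment-policy summary, and add patient-time at risk and events per patient-year.
3. Add a by-arm table that splits events by onset before or after the start of ADT or other systemic therapy, with time at risk in each period and recorded attribution shown.
4. If an early window is also reported, give it the same length in both arms, make it long enough to cover the last infusion with permitted delays plus 30 days (Day 181 plus 30 may not), and report time at risk in it.

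**Cost.** SAP wording and one or two tables. Event onset is already a recorded variable (section 10.5.1.1), and the ADT start date is needed for ADT-free survival. The drawbacks are a longer safety output and imprecise rates with about 32 men per arm. Patient-time will not correct unequal detection from the extra monthly blood counts in the combination arm (section 6.7.1), so the table should carry a note on that.
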